## 1 Introduction

#### 1.1 Background

Triggerise has designed a web and phone based platform Named 'Tiko Explore' to digitally empower young girls and women in lower-income groups at scale, and connect them to the products, services and information that will improve their health and wellbeing, supporting local economies and building private sector service provider networks in the process. Triggerise employs a digital platform that connects consumers to health clinics, pharmacies, mobilizers and local small businesses—giving them both the power to access health information and services on their own terms. Building on these relationships, the platform uses principles of behaviour economics to motivate consumers to make positive choices by providing incentives and discounts, rewarding continued use of products etc.

Employing tried and tested marketing principles - including rewards, promotions, discounts, coupons, reminders, alerts etc., the platform has encouraged over 85,000 young women Rajasthan, Uttar Pradesh and Delhi to take up almost 150,000 sexual, reproductive and maternal health services. By linking the demand and supply sides of the market, our platform grows Sexual Reproductive Health (SRH) and maternal and child health (MCH) demand while enhancing user choice.

Example of (SRH) services and products include: (a) contraceptives such as OTC pills, condoms, diaphragm, etc; (b) family planning services such as medical counselling, IUD insertion/removal, etc; and (c) hygiene products such as sanitary pads. Example of MCH ) services include: (a) linking with medical professionals/gynaecologists for ANC check-up, laboratory testing; (b) linking to pharmacy for IFA and other supplements as prescribed by doctors; and (c) OTC products for mother and children from pharmacy.

The users use Tiko card to get substantial discounts as well as earn 'Tiko miles' which are redeemable as payment towards above products. The Pro agent is also allowed to buy hygiene products at bulk and at heavy discounts and sell them to beneficiaries. More information about the Tiko Platform (the intervention or the programme) is given in **Annexure 4**.

#### 1.2 Research objective

Triggerise has commissioned an independent impact assessment of the platform to understand what values and benefits are derived at the end user level – both health impacts at the beneficiary level and economic impact at the 'agent' level who is responsible to onboard the beneficiary on the platform and link them with services. The study also aims to gain insights on the merits of the various platform features and their efficacy. Triggerise expects the research organization to publish the findings of the study in an international journal.

#### 1.3 Key Research Questions

Key questions include, but are not limited, to the following for beneficiaries of the Toko platform – women who use SRH and MCH products and services.

#### 1. Health Impact and users perception

- Do users take up SRH and maternal health products and services because of our innovation or regardless of it? (In other words, are we stimulating new SRH users or are the members previously active SHR clients?)
- When they first enrolled in the program, were they using contraceptives or are their first-time users? Did the platform make it easier for them? How? What other benefit appeal? If they were switchers, what were the motivators to switch from their previous source of health services to ours?
- How often did they use the platform? If they were repeat users, what was their motivation to come back to the platform? If they were only one time users, why did they not come back?
- Does the Tiko digital platform increase consistent use of short-term contraceptive methods? Why or why not?
- Does the Tiko digital platform increase consistent MNCH behaviours? Why or why not?
- What did they like about the platform and the experience? What barriers did it solve for them? Will they use it again? Will they recommend their friends to use?
- Why did they choose Tiko platform? What would they have done if it were not available as an option?
- What perception or behaviour shifts have our intervention been able to address around stigma, access, privacy, dignity/respect, willingness to pay, etc?

#### 2. Cost per user/health uptake and benchmarking

- How cost effective is our innovation compared with other projects focused on SRH and MNCH service uptake in India, particularly in the private sector?
- Impact of our services in terms of DALYs, CYPS, pregnancies averted using exiting data and models such as IMPACT and LIST2.

## 2 Research Methods

### 2.1 Overview of methods

This evaluation will be a mixed methods observational design with mainly descriptive and exploratory analysis. The desk research will review documents, secondary data public available (such as NFHS), and any App background data (deidentified) to better understand the programme.

This is followed by qualitative surveys for which 40 in-depth interviews of various beneficiaries and programme stakeholders (demand creators, service providers, lifestyle partners) will be conducted in person or over phone.

Depending on the insights, we will develop a structured quantitative questionnaire and administer the in-person survey to approx. 480 beneficiaries of SRH and MCH services (total). These surveys will seek information on knowledge, practices, barriers, enablers for SRH and MCH services, exposure o Tiko platform, and how it helped or did not help. The survey participants will be women (18-35years of age) who had subscribed to Tiko card between 2018 and 2020. A subset of these would be regular users, a subset will be sporadic

or one-time user and remaining will be 'non-users'. The sample will try to get adequate representation from all categories.

The in-person surveys will be followed with shorter (10-15 minutes) phone surveys with 1200 active users and 600 non-users who had enrolled on Tiko platform. Phone surveys will collect only basic information needed to confirm findings from in-person and qualitative surveys.

The analysis will triangulate the insights from both qualitative and quantitative analysis. We mainly anticipate descriptive analysis to tabulate indicators related to knowledge, practices, barriers, enablers w.r.t. SRH and MCH services, exposure and use of Tiko platform, how it has helped or not helped or affected their well being, suggestions and preferences for different components of the platform, etc. We anticipate cross tabulation by socio-economic characteristics, regions (say by Cities), and duration of use.

While no analytical tests are anticipated at this time, we expect to conduct standard bivariate tests (t-test and chi2 test) and regression analysis for more nuanced group mean tests or multiple comparison tests (logit, OLS, mixed models). We will be adjusting for standard errors for robust inference. In case of statistical inference, we expect one side test with alpha < 0.1 to consider a relationship or test statistic significant.

For cost effectiveness analysis, we will use existing (and publicly available) models such as LIST 2 and Impact. These models will need as inputs data on type and number of contraceptives and family planning services, and number of women who have completed ANC protocol of at least 4 visits. The rest of the inputs and data is in-built in the model to estimate Couple of Years of Protection (CYP) and DALYs. The data needed is available as App backend data without any identifiable information of the respondents such as address, name, phone number. The researchers will only know about the city and age of the beneficiaries along with details of their each transaction on Tiko platform – which service pr product, from which service provider, date, and quantum of purchase if any.

Then, a quantitative health-impact analysis will be done using insights from qualitative research. The insights will then be used by for a CEA and CBA based on primary and secondary data.

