For cost effectiveness analysis, we will use existing (and publicly available) models such as LIST 2 and Impact. These models will need as inputs data on type and number of contraceptives and family planning services, and number of women who have completed ANC protocol of at least 4 visits. The rest of the inputs and data is in-built in the model to estimate Couple of Years of Protection (CYP) and DALYs. The data needed is available as App backend data without any identifiable information of the respondents such as address, name, phone number. The researchers will only know about the city and age of the beneficiaries along with details of each transaction on Tiko platform – which service pr product, from which service provider, date, and quantum of purchase if any.

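### CYP, DALY and cost-effectiveness results are built from platform transaction counts and called impact, with no stated step for additionality; they are gross unless the models already adjust

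*Protocol*

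**What the plan says.** **Inputs.** Section 2.1 names LIST 2 and Impact as the models: "These models will need as inputs data on type and number of contraceptives and family planning services", together with the number of women with four or more antenatal (ANC) visits. Both are to come from de-identified App backend data. Section 2.6 repeats this and adds nothing on attribution: "The rest of the inputs and data is in-built in the model to estimate Couple of Years of Protection (CYP) and DALYs".

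**What the backend data hold.** Section 2.1: "The researchers will only know about the city and age of the beneficiaries along with details of their each transaction on Tiko platform".

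**How the output is described.** Section 1.3, second group of questions: "Impact of our services in terms of DALYs, CYPS, pregnancies averted using exiting data and models such as IMPACT and LIST2". The same group asks: "How cost effective is our innovation compared with other projects focused on SRH and MNCH service uptake in India".

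**Where additionality appears.** Section 1.3, first group: "Do users take up SRH and maternal health products and services because of our innovation or regardless of it". It also asks about first-time users, about switchers, and about what women would have done had the platform not been available. Section 2.2 plans a comparison of regular users with one-time or non-users and calls the additionality question exploratory.

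**The possible link.** Section 2.1 ends with two sentences. One announces a quantitative health-impact analysis informed by the qualitative work. The other reads: "The insights will then be used by for a CEA and CBA based on primary and secondary data". Section 2.6 has neither sentence.

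**The concern.** A service recorded on the platform is not the same as a service caused by it. The platform offers discounts and redeemable rewards (Section 1.1), so a woman already using contraception or antenatal care has a reason to move her purchases onto it. The protocol expects this, since it asks about switchers. Yet the models are to be fed with all recorded volumes and the result is called impact.

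If nothing removes substitution, care that women would have obtained anyway is credited to the platform. CYPs and DALYs are then too high for the recorded services and cost per unit is too low, which favours the organisation that commissioned the study and expects journal publication. The comparison with other projects is also fair only if both sides are gross or both are net, and no basis is set.

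**Working it through.** The protocol states no CYP, DALY, cost or additional share, so there is no figure to reproduce. The check is a reading of the passages, followed by the algebra of gross against net.

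**Step 1. Trace the additionality answer.**

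| Element | Where | Counterfactual content |
|---|---|---|
| Contraceptive and service volumes, women with four ANC visits | 2.1, 2.6 | None: recorded counts |
| All other model inputs | 2.1, 2.6 | Built in; content not described |
| Backend fields | 2.1, 2.6 | City, age, transactions; no prior use or prior source |
| Prior use, switching, what women would have done | 1.3 | Yes, but not linked to the models |
| Regular users against one-time or non-users | 2.2 | Exploratory, not linked to the models |
| Health-impact analysis, then CEA and CBA | end of 2.1 | Leaves room for a link; names none |

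The information on additionality and the model inputs sit in separate data sources, and no stated step joins them. As described, the backend data alone cannot supply the missing quantity.

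**Step 2. Size, if the models do not adjust.** For service type k, let n_k be the recorded volume, w_k the CYPs or DALYs per unit, and a_k the share that would not have occurred without the platform.

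- Gross: G = Σ n_k w_k
- Net: N = Σ n_k w_k a_k
- Additional share: a = N/G, so G/N = 1/a
- With the same total cost C, gross cost per unit is C/G = a × C/N, an understatement of 1 − a

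| Assumed a | Net per 1,000 gross | Overstatement 1/a | Cost per unit understated by |
|---|---|---|---|
| 1 | 1,000 | 1.00 | 0% |
| 0.75 | 750 | 1.33 | 25% |
| 0.5 | 500 | 2.00 | 50% |
| 0.25 | 250 | 4.00 | 75% |

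The values of a are assumptions. Because a is weighted by volume and by w_k, it is not the proportion of women who say they are new users.

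**Step 3. The opposite direction.** The table concerns recorded services only. The ANC input counts women with at least four visits, but the backend sees only platform transactions. A woman who completes her visits partly on and partly off the platform may not be counted as reaching four. That would lower the ANC count, by an amount the documents do not give.

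**Step 4. Reach of a survey-based share.** Section 2.1 limits the survey to women aged 18–35 who subscribed between 2018 and 2020, while Section 3 gives platform users as 18–45. The in-person survey covers only Agra and Jaipur: (21,743 + 28,531)/62,060 = 81.0% of the users in the Section 2.3 table. Expected response in Section 2.3 is 30–40% in person and 10–15% by phone.

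**The case against.** - **The models may already adjust.** The built-in inputs are not described, so no overstatement is proved. This stands: every consequence above is conditional on it, and checking the models comes first.
- **This is detail for an analysis plan, and Section 2.1 leaves room for it.** Primary data can include the surveys, and the closing sentences could cover an adjustment. That stands in part. But the protocol itself fixes the inputs, their source and the name of the output, and followed as written these do not answer its own first research question.
- **The impact label is only a research-question bullet.** The study is described as mainly descriptive and exploratory, and not as a controlled trial. True, and it limits how much weight the word carries. It is still the only description given of what the model output means.
- **The bias need not run one way.** Correct for the ANC count (Step 3).
- **A net figure could be less reliable than a clearly labelled gross one.** It would rest on self-report at low response. This supports showing it beside the gross figure as exploratory, not in its place.

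**Conclusion.** The point holds as a conditional one. The stated inputs are gross volumes, the output is called impact, and no stated step brings additionality in. If the built-in inputs do not remove substitution, results for recorded services are overstated by 1/a: 1.0 to 4.0 over the assumed range of 1 down to 0.25. The true size is unknown, and partial off-platform ANC could offset some of it.

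Three stronger readings are tempting and are not supported:

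- *That the results will certainly be inflated.* The documents do not describe what the models adjust for.
- *That the power contrasts in Section 2.2 reveal the share.* A reader might compute 0.125/0.625 = 20% (factor 5.0) or 0.075/0.575 = 13% (factor 7.7). Those are differences the survey is sized to detect, not estimates, and they would need non-users to be a valid counterfactual for users who selected themselves.
- *That a number of non-additional services can be read off the Section 1.1 totals.* That background sentence ("the platform has encouraged over 85,000 young women Rajasthan, Uttar Pradesh and Delhi to take up almost 150,000 sexual, reproductive and maternal health services") gives a raw count, to which a CYP- or DALY-weighted share does not apply.

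**What to change.** In Sections 2.1 and 2.6:

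1. Check and state what the models' built-in inputs adjust for. If they do not remove substitution, label results from backend counts as gross, not as impact.
2. Beside them, report a net result as an exploratory sensitivity analysis. Take the additional share from the questions planned in Section 1.3 on prior use, switching and what women would have done otherwise, weighted by service type and volume where possible. Carry its uncertainty through the model, together with a wide range of assumed shares up to 1. Say which users the share covers, and note that ANC completed partly elsewhere may be missed.
3. Compare with other projects gross with gross or net with net, and say which.

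The cost is a few lines of text, a check of the models and a small amount of extra analysis. The estimates will be less favourable and wider. The net figure will rest on self-report, on the low expected response and on a survey population narrower than the backend data, and should be presented with those limits.

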#### 2.2 Sample Design and Power Calculations

For detailed 45-50 minutes in-person surveys, 570 respondents will be interviewed across Rajasthan, Uttar Pradesh and Delhi, of which we expect to complete 480 interviews. This sample size was determined on basis of measuring a proportion of 50% with 5 pp error rate and 95% confidence which yields n of 384 and this n was increased by design effect of 1.25 to account for clustering if any at the city level. In person surveys will be done in Agra, Jaipur

For phone surveys, we designed a sample of 2000 complete surveys. Moreover, over sampling will be done in Rajasthan, Uttar Pradesh and Delhi to ensure at least 50 interviews in each city. This sample is designed such that we can conduct descriptive analysis for 3-4 sub-groups (say by cities or by socio-economic categories) with at least 300-400 sample in

each sub-group. The purpose of phone surveys will be to add more statistical power to limited in-person sample size we have for few key questions of interest.

We also expect that the phone surveys and in-person data will be used for statistical group mean tests between regular users and one-time or non-users to compare SRH and ANC related practices between the two groups. It is not a controlled trial of Tiko platform but will be exploratory to understand additionality in service usage of regular users if any.

Assuming at least 150 regular and 150 non-users included in the in-person surveys, the sample will have power to detect 25% relative change or 0.25 SD change from an outcome distributed binomially with mean of 0.50 or with standardized normal distribution with mean 0 and SD of 1 N $^{\circ}(0,1)$  with power of 80% and Type I error of 0.10 with one sided test.

Assuming 500 regular and 500 non-users included in the in-person surveys, the sample will have power to detect 15% relative change or 0.15 SD change from an outcome distributed binomially with mean of 0.50 or with standardized normal distribution with mean 0 and SD of 1 N~(0,1) with power of 80% and Type I error of 0.10 with one sided test.

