#### 2.3 Sampling for In-Person and Phone-Surveys

The sample frame for both surveys will be the Tiko beneficiary database available with Triggerise. Below is the summary of viable database sample frame (exclude smaller sites where the programme is too small to be considered in this study)

Stata	City	Area	Number of		
Sidle			Enrollments	Actual Users	Non-Users
Uttar Pradesh	Agra	Both	34,726	21,743	12,983
Rajasthan	Jaipur	Both	29,588	28,531	1,057
Rajasthan	Ajmer	Urban	7,325	4,532	2,793
Rajasthan	Tonk	Peri Urban	5,176	3,993	1,183
Delhi	Delhi	Urban	3,846	3,142	704
Uttar Pradesh	Firozabad	Peri Urban	1,044	119	925
TOTAL			81,705	62,060	19,645

The following steps will be followed for sampling of in-person survey respondents:

- 1. Restrict the study to only Jaipur and Agra which constitutes 70% of the enrollments and 84% of the actual user base.
- 2. Stratify sample as 150 non-users (enrollment minus users) and 350 users
- 3. Distribute sample in approx. proportion to the actual numbers in both cities for users and non-users as below.

City	Non-users	Actual Users	Total
Agra	100	150	250
Jaipur	50	200	250
Total	150	350	500

- 4. Distribute the sample across the 'Tiko Pro Agents' working in the city. We currently don't have this data, but we expect to complete at least 5 interviews per agent and spread the sample to cover about 25% of the agents working in the city.
- 5. Based on above, randomly sample the Pro Agents from database that will be made available by Triggerise.
- 6. Obtain a list of randomly sampled Beneficiaries from Triggerise for each sampled pro agent. We will obtain 3-times the number of completed interviews required per agent because our scoping visit suggests expecting 30-40% response rate in finding the beneficiary house with help of agent and then getting their consent for the interview. If required, Triggerise will make available more beneficiaries (their name and phone numbers per agent) if the sample size is not achieved.
- 7. NEERMAN enumerators will call each beneficiary sequentially in the list and fix appointments for the in-person interview. The phone records will track validity of numbers, refusals, and consents. Pro agent's help will be sought to find address or in field logistics or to establish our enumerators' bona fides.

The following steps will be followed for sampling of phone-survey respondents:

- 1. Exclude Firozabad which has no programme in 2020

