- 2. Stratify sample as 500 non-users (enrollment minus users) and 1500 users
- 3. Distribute sample in proportion to the actual numbers as below.

City	Non-users	Actual Users	Total
Agra	347	527	873
Jaipur	28	691	719
Ajmer	75	110	184
Tonk	32	97	128
Delhi	19	76	95
Total	500	1500	2000

- 4. Obtain a list of randomly sampled Beneficiaries as above. We will obtain 10-times the number of completed interviews required per agent because our scoping visit suggests to expect 10-15% response rate in phone surveys. If required, Triggerise will make available more beneficiaries (their name and phone numbers per agent) if the sample size is not achieved.
- 5. NEERMAN enumerators will call each beneficiary sequentially in the list and fix appointments for the phone interview. The phone records will track validity of numbers, refusals and consents. Pro agent's help will be sought to establish our enumerators' bona fides if needed.

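### The 1.25 design effect is assigned to city, but the sampled cluster is the Pro Agent, so the 5 pp margin from 480 interviews is not assured

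*Protocol*

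**What the plan says.** Protocol section 2.2 sizes the in-person survey by "measuring a proportion of 50% with 5 pp error rate and 95% confidence which yields n of 384". It adds that "this n was increased by design effect of 1.25 to account for clustering if any at the city level" and arrives at 570 approached, "of which we expect to complete 480 interviews".

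Section 2.3 then describes the in-person sampling. Step 1 is "Restrict the study to only Jaipur and Agra", and step 3 allocates 250 interviews to each city, split by user status. Step 4 spreads the sample over the Pro Agents: "we expect to complete at least 5 interviews per agent", covering roughly a quarter of the agents in each city. The same step says that the agent data are not yet available. Step 5 is to "randomly sample the Pro Agents from database that will be made available by Triggerise", and step 6 draws women at random within each sampled agent.

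On inference, sections 2.1 and 2.6 say only "We will be adjusting for standard errors for robust inference" and list mixed models among the possible methods. For the phone survey, step 4 of section 2.3 refers back to the in-person procedure and says "We will obtain 10-times the number of completed interviews required per agent".

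**The concern.** The sample-size statement and the sampling steps describe different designs. Two cities taken on purpose, each with a set number of interviews, are strata and add no between-city sampling variance. The extra variance arises at the unit that is drawn at random and contributes several women, which is the Pro Agent. Section 1.2 describes the agent as the person who enrols women and links them to services, so women under one agent may well resemble each other on service use and on views of the platform.

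The 1.25 is the only allowance for clustering behind the 480. If it is not tied to the agent, nothing in the protocol links it to the number of women per agent or to how alike they are. The stated 5 pp margin would then have no demonstrated basis. Unlike an analysis detail, the load per agent cannot be changed once the interviews are done.

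**Working it through.** **Inputs from the protocol.** p = 0.50, margin 5 pp, 95% confidence, design effect 1.25 and 480 completed interviews (section 2.2). Two fixed cities, 250 interviews each, at least 5 per agent and about 25% of agents (section 2.3). The ICC and the agent count are not given. ICC values of 0.02, 0.05 and 0.10 are assumed below, and m is varied.

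**The plan's own figure.** n = 1.96² × 0.25 / 0.05² = 384.15, and 384.15 × 1.25 = 480.2. Both stated numbers reproduce, so the arithmetic is sound. The question is what the 1.25 stands for.

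**Read as a city effect.** With DEFF = 1 + (m − 1) × ICC and 240 women per city, 1.25 corresponds to an ICC of 0.25 / 239 ≈ 0.001. The figure has no natural meaning here, because the cities are not sampled.

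**Read as an agent effect.** 1.25 suffices if (m − 1) × ICC ≤ 0.25, so the break-even ICC is 0.25 / (m − 1). The half-width at 480 interviews is 1.96 × √(0.25 × DEFF / 480). For example, m = 10 and ICC = 0.05 give DEFF = 1.45 and a half-width of 5.39 pp. The interviews needed to hold 5 pp are 384.15 × DEFF, rounded up.

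| m | Break-even ICC | Half-width in pp (n needed), ICC 0.02 | ICC 0.05 | ICC 0.10 |
|---|---|---|---|---|
| 5 | 0.0625 | 4.65 (415) | 4.90 (461) | 5.29 (538) |
| 10 | 0.028 | 4.86 (454) | 5.39 (558) | 6.17 (730) |
| 20 | 0.013 | 5.25 (531) | 6.25 (750) | 7.62 (1,115) |

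**What sets m.** With 250 interviews per city and 25% of agents covered, m = 250 / (0.25 × agents in the city). For illustration, 200 agents give m = 5, 100 give m = 10 and 40 give m = 25. The coverage rule therefore fixes the average load, but only through a count that the protocol does not have.

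**Unequal loads.** With DEFF = 1 + ((1 + CV²) × m − 1) × ICC, the break-even at a mean of 5 per agent falls from 0.0625 to 0.048 (CV 0.5) or 0.035 (CV 0.8).

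**Using the 500 interviews of section 2.3 instead of 480.** The break-even rises to 0.075 at m = 5 and 0.034 at m = 10.

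**The case against.** The strongest reply is that the 1.25 may be adequate in practice. Any pair with (m − 1) × ICC = 0.25 produces it, such as m = 6 with 0.05 or m = 10 with 0.028. Lower correlations leave room to spare: m = 10 with an ICC of 0.02 gives 4.86 pp. The 25% coverage target limits the average load once agents are counted, section 2.3 allocates 500 rather than 480, and the study calls itself mainly descriptive and exploratory. All of this stands. It means that the 5 pp margin has not been shown to fail, and that no particular ICC can be attributed to the plan.

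A reader might also infer that standard errors will be clustered on two cities, which would be unusable. The protocol does not support that. City is named only in the sample-size sentence. Sections 2.1 and 2.6 name no level for the adjustment, and that detail may properly sit in an SAP that is not shown.

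For the phone survey, a reader might infer that no agent stage exists and that the reference to agents is a slip. The step's reference back to the in-person procedure may equally carry the agent stage over, so the text is ambiguous rather than wrong.

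None of this answers the main point. The protocol itself fixes both the level of the design effect and the sampling stages, and the two disagree.

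**Conclusion.** The point holds in a limited form. The design effect is tied to a level at which nothing is sampled, and the level that is sampled has no stated ICC, no ceiling on interviews and no known number of agents. The 5 pp margin is therefore unsupported, though not disproved. At 5 women per agent it is met for any ICC up to 0.0625. At 20 per agent it is missed at all three assumed values, with half-widths of 5.25, 6.25 and 7.62 pp.

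These figures rest on assumed ICCs, 480 completed interviews, p = 0.50, equal weights, equal loads per agent (except where a CV is given) and no finite-population correction for agents. Such a correction would loosen the limits somewhat but would not remove their dependence on m and the ICC. The correction is worth making before the agents are drawn.

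**What to change.** - **Section 2.2:** attach the design effect to the Pro Agent, and state the assumed ICC and the target m that produce it.
- **Section 2.3, in-person step 4:** replace the open-ended floor with a target or maximum, about 5 per agent where the number of agents allows, and let the share of agents covered follow. Five per agent needs 250 / 5 = 50 agents per city. If a city has fewer, accept a larger m and restate the margin, or raise n.
- **Section 2.6:** use the Pro Agent as cluster and city by user status as strata for in-person standard errors. Keep a de-identified agent code in the analysis file so that this can be done.
- **Section 2.3, phone step 4:** say whether the reference back to the in-person steps and the mention of agents mean that agents are sampled there too. If so, cluster on agent in that survey as well.

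The cost is mainly wording. Field teams may have to visit more agents, or the stated margin becomes slightly wider. A cap of 5 does not by itself guarantee 5 pp, since an ICC of 0.10 would still give 5.29 pp. The assumed ICC therefore needs to be stated alongside it.
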